- y) Obinutuzumab ADA and PK samples to be taken only in Cycle 5 and 7 before administration of RO7172508.
- z) sCEA to be assessed for enrollment in cohorts with RO7172508 doses < 12 mg.
- aa) PD blood flow cytometry to be taken from Cycle 5 onwards only at Cycles 8,12 and 16 at predose

Table 3 Part II: Multiple Participant Cohorts SC QW/Multiple Ascending Dose-Escalation

Cycle (21 days)	Screening ^x	Cycle 1								Cycle 2 - 4 ^a				Cycle 5 onwards ^a				End of Treatment	Safety Follow-Up	Survival Follow-Up ^r	Unscheduled (Safety)
Day	D-28 to D-1	Day 1	Day 2	Day 3	Day 5 ^t	Day 8	Day 10 ^o	Day 15	Day 17	Day 1	Day 5 ^f	Day 8	Day 15	Day 1	Day 5 ^z	Day 8	Day 15				
Assessments ^a		pre-dose	24 hrs post dose (±2 hrs)	48 hrs post dose (±4 hrs)	96 hrs post dose (±5 hrs)	pre-dose	48 hrs post dose (±4 hrs)	pre-dose	48 hrs post dose (±4 hrs)	pre-dose	96 hrs post dose (±1 day)	pre-dose	pre-dose	pre-dose	96 hrs post dose (±5 hrs)	pre-dose	pre-dose	incl. early discont. visit (e.g. progressive disease)	60 days after last treatment	90 Days after last treatment then every 3 mths ^r	e.g. In the event of an IRR ≥G2 ⁿ
Informed Consent ^b	X																				
Eligibility	X																				
Demography	X																				
Medical History	X																				
Pulmonary Function Tests ^w	X																				
Archival Tissue ^h	X																				
Previous and Concomitant Treatments		X																			
Adverse Events		X																			
Physical Examination	X	X								X				X				X	X		X
Anthropometric Measurements ^q	X	X								X				X					X		
Vital Signs ^v	X	X	X	X	X	X	X	X	X	X	X	X	X	X	X	X	X	X	X	X	X
ECOG Performance Status	X	X								X				X				X	X		X
ECG-12 lead ^d	X	X			X					X	X			X ^d				X	X		
Pregnancy Test ^e	X									X				X					X		

Table 3 Part II: Multiple Participant Cohorts SC QW/Multiple Ascending Dose-Escalation (cont.)

Cycle (21 days)	Screening ^z	Cycle 1								Cycle 2 - 4 ^a				Cycle 5 onwards ^a				End of Treatment	Safety Follow-Up	Survival Follow-Up ^r	Unscheduled (Safety)
Day	D-28 to D-1	Day 1	Day 2	Day 3	Day 5 ^t	Day 8	Day 10 ^o	Day 15	Day 17	Day 1	Day 5 ^r	Day 8	Day 15	Day 1	Day 5 ^{c,t}	Day 8	Day 15				

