- l To allow estimation of tumor growth rate before start of treatment an exploratory assessment of tumor kinetics will be made by comparing post treatment scans with at least 2 pre-treatment scans not older than 12 weeks prior to C1D1 if available. One of the pre-treatment scans will be the study baseline scan taken during screening and the second will be within the preceding 12 weeks.*
- m Obinutuzumab to be administered either on Day-7 (2000 mg) or on Day-7 and Day-6 (1000 mg each day). If obinutuzumab is given only on one day, then the schedule for Day-7 should be followed including an end of infusion sample.*
- n Samples should be taken BEFORE obinutuzumab is administered.*
- o sCEA to be assessed for enrollment in cohorts with RO7172508 doses < 12 mg.*
- p Sample to be taken end of infusion only*

Table 7 Schedule of Assessments Part II: Multiple Participant Cohorts SC Q3W

Cycle (21 days)	Screening ^x	Cycle 1 - 2						Cycle 3 - 4 ^a				Cycle 5 onwards ^a			End of Treatment	Safety Follow-Up	Survival Follow-Up ^q	Unscheduled (Safety)	
Day	D-28 to D-1	Day 1	Day 2	Day 3	Day 5	Day 8	Day 15	Day 1	Day 3 ^p	Day 8	Day 15	Day 1	Day 3 ^{c, p}	Day 15					
Assessments ^a		pre-dose	24 hrs +/- 2 hrs	48 hrs +/- 4 hrs	+/- 1 day			pre-dose	48 hrs +/- 1 day			pre-dose	48hrs +/- 4 hrs		incl. early discont. visit (e.g. progressive disease)	60 Days after last treatment (+/- 5 Days)	90 Days after last treatment then every 3 mths ^q	e.g. In the event of an IRR ≥G2 ^o	
Informed Consent ^b	x																		
Eligibility	x																		
Demography	x																		
Medical History	x																		
Pulmonary Function Tests ^w	x																		
Archival Tissue ^h	x																		
Previous and Concomitant Treatments	x	x	x	x	x	x	x	x	x	x	x	x	x	x	x	x	x	x	x
Adverse Events	x	x	x	x	x	x	x	x	x	x	x	x	x	x	x	x	x	x	x
Physical Examination	x	x						x				x			x	x			x
Anthropometric Measurements ^s	x	x						x				x			x	x			x
Vital Signs ^v	x	x	x	x	x	x	x	x	x	x	x	x	x	x	x	x			x

Table 7 Schedule of Assessments Part II: Multiple Participant Cohorts SC Q3W (cont.)

Cycle (21 days)	Screening ^x	Cycle 1 - 2						Cycle 3 - 4 ^a				Cycle 5 onwards ^a			End of Treatment	Safety Follow-Up	Survival Follow-Up ^q	Unscheduled (Safety)
Day	D-28 to D-1	Day 1	Day 2	Day 3	Day 5	Day 8	Day 15	Day 1	Day 3 ^p	Day 8	Day 15	Day 1	Day 3 ^{c, p}	Day 15				

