o	Sample to be taken only if \geq Grade 2 the safety event is suspected to be immune-related (e.g., IRR). Refer to Table 5 for additional assessments if safety event is an IRR/CRS (\geq Grade 3) that requires tocilizumab treatment. Any biopsy samples or results done as part of standard of care can be shared with the Sponsor if applicable.
p	The Day 3 visit may be adjusted +/- 1 day depending on safety and PD data. The visit optimal timepoint will be communicated to the Investigators for consistency and should occur \pm 4 hrs from each complete day of administration (i.e. 24hrs \pm 4hrs; 48 hrs \pm 4hrs; OR 72hrs \pm 4hrs).
q	Survival follow-up visit to be performed 90 days (\pm 7 Days) after the last treatment either in person or a phone call to document any ongoing or resolved AEs, and every 3 months (\pm 2 weeks) thereafter for overall survival.
r	Serology (as per local regulations) includes HIV, hepatitis B surface antigen, total hepatitis B core antibody, hepatitis C virus antibody. Results must be obtained and reviewed prior to administration of RO7172508.
s	Weight to be recorded pre-infusion. Height to be measured at screening only.
t	Required for Cycle 5 only.
u	Samples to be collected only in Cycle 1
v	Vital signs include systolic and diastolic blood pressure; pulse rate; temperature; respiratory rate and oxygen saturation.
w	Pulmonary function tests should include spirometry; forced expiratory volume (FEV1), forced vital capacity (FVC) and Diffusion capacity (DLCO).

Table 7 Schedule of Assessments Part II: Multiple Participant Cohorts SC Q3W (cont.)

x	Refer to Table 6 in the event obinutuzumab pre-treatment is implemented for specific additional assessments during the screening period.
y	Obinutuzumab ADA and PK samples to be taken only in Cycle , 5 and 7 before administration of RO7172508.
z	sCEA to be assessed for enrollment in cohorts with RO7172508 doses < 12 mg.
aa	PD blood flow cytometry to be taken from Cycle 5 onwards only at Cycles 8,12 and 16 at predose

2. **INTRODUCTION**

2.1 **STUDY RATIONALE**

RO7172508 is a novel T-cell bispecific (TCB) antibody that targets carcinoembryonic antigen (CEA) expressed on tumor cells and cluster of differentiation 3 (CD3) epsilon chain (CD3e) present on T-cells.

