
 To estimate depth and duration of response on target lesion size due to RO7172508 and the effect on the risk of appearance of new lesions during treatment by tumor kinetic modeling 	
 Sum of lesion diameter from computed tomography (CT) scans

 To assess ADA specificity 	
 Development of ADAs directed against either the CEA or CD3 binding moiety.

 To make a preliminary assessment of the efficacy of tocilizumab (Actemra®/RoActemra®) in ameliorating the symptoms of severe CRS following RO7172508 treatment, if data allows. 	
 Changes in the nature and severity of CRS following administration of tocilizumab for severe CRS.

 To assess the incidence of anti-drug antibodies (ADAs) against obinutuzumab (if applicable) 	
 Presence or absence and titer of ADAs Serum concentration of obinutuzumab

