6.1 TREATMENTS ADMINISTERED

Table 11 summarizes the treatments administered.

Table 11 RO7172508 Summary of Treatments Administered

Study Treatment Name:	Part I RO7172508	Part II RO7172508
Dosage Formulation:	Solution for infusion and injection	Solution for infusion and injection
Unit Dose Strength(s)/Dosage Level(s):	20 mg/mL	20 mg/mL
Dose:	65 µg up to a maximum of 1.6 mg	1.6 mg up to a maximum of 400 mg IV 2 mg up to a maximum of 160 mg SC
Route of Administration:	IV	IV and SC
Dosing Instructions:	see Pharmacy Manual	see Pharmacy Manual
Packaging and Labeling:	Study treatment will be provided in a carton box (one labeled vial per box). Each carton box will be labeled as required per country requirement.	Study treatment will be provided in a carton box (one labeled vial per box). Each carton box will be labeled as required per country requirement.

Guidelines for dosage modification and treatment interruption or discontinuation are provided in Section 6.6 or Section 7, respectively.

Please see the [RO7172508 Investigator's Brochure](#) and Pharmacy Manual for more details.

Administration of Obinutuzumab

The obinutuzumab Drug Product will be supplied by the Sponsor as a 50 mL single dose glass vial containing 1000-mg liquid concentrate in 40 mL (25 mg/mL) for infusion. In addition to the drug substance, the liquid is also composed of histidine/histidine-HCl, trehalose and poloxamer 188 (see Table 12).

Obinutuzumab will be administered either as a single dose of 2000 mg 7 days (D-7) before the first dose of RO7172508 (C1D1) or two doses of 1000 mg over days 6 and 7 days (D-6 and D-7) before the first dose of RO7172508 (C1D1).

For information on the formulation and handling of obinutuzumab, refer to the pharmacy manual and Obinutuzumab [Investigator’s Brochure](#).

Table 12 Obinutuzumab Summary of Treatment Administered

Study Treatment Name	Obinutuzumab
Dosage Formulation	Concentrate for solution for IV infusion
Unit Dose Strength(s)/Dosage Level(s)	25 mg/mL
Dose	2000 mg or split doses of 2x 1000 mg
Route of Administration	IV
Dosing Instructions	see Pharmacy Manual
Packaging and Labeling	Study treatment will be provided in a carton (one labeled vial per box). Each carton will be labeled as required per country requirement.

Administration of Tocilizumab

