8.5.1 Immunogenicity Assessments

As RO7172508 is a human antibody, there is a risk that ADAs against RO7172508 could develop, potentially reducing its efficacy and/or potentially resulting in symptomatic hypersensitivity reaction, in particular immune-complex reactions.

Antibodies to RO7172508 will be evaluated in blood samples collected from all participants according to the SoA (Section 1.3). Additional ADA samples should also be collected at the time of treatment discontinuation or at the safety follow-up visit. In each case, for each collected ADA sample, a corresponding PK sample will be collected at the same time-point for the determination of the RO7172508 concentration. *Participants experiencing a Grade ≥ 3 toxicity potentially related to ADAs will not be further treated with RO7172508 (see Section 7.1).*

Validated screening, confirmatory, and titer assays will be employed to detect ADAs against RO7172508. The date and time of each sample will be recorded in the eCRF.

Remaining volumes of ADA samples may also be used for assay development or validation, for compound-related exploratory analyses, or to help develop further blood tests, after they are used for the mentioned intended uses.

Antibodies to obinutuzumab will be evaluated in all participants who receive obinutuzumab as pre-treatment according to the SoA.

The PK/ADA samples will be destroyed within 2 years after the date of final CSR, unless the participant agrees to participate in the RBR.

Details on sampling procedures, sample storage, and shipment are given in the Study Flow Chart and Laboratory Manual.

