9.3 POPULATIONS FOR ANALYSES

For purposes of analysis, the following populations are defined in [Table 21](#).

Table 21 Analysis Populations

Population	Description
Efficacy	All participants who received at least one dose of RO7172508.
Safety	All participants enrolled in the study who received at least one dose of study treatment (RO7172508 and/or obinutuzumab if applicable) will be included in the safety population. Unless otherwise specified, the safety population will be the default analysis set used for all analyses.
DLT evaluable	DLT-evaluable participants are those who have completed the DLT window without a DLT, or participants who reported with a DLT. This population will be used in the determination of the MTD.
Pharmacokinetic	All participants who have received at least one dose of study treatment and who have data from at least one post-dose sample will be included in the PK analysis population. Participants will be excluded from the PK analysis population if they significantly violate the inclusion or exclusion criteria, deviate significantly from the protocol, or if data are unavailable or incomplete which may influence the PK analysis. Excluded cases will be documented together with the reason for exclusion. All decisions on exclusions from the analysis will be made prior to database closure.
Immunogenicity	Participants who had at least one pre-dose and one post-dose ADA assessment will be included and analyzed according to the treatment they actually received. The relationship between ADA status and safety, efficacy, PK, and biomarker endpoints will be analyzed and reported descriptively via subgroup analyses.

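### Obinutuzumab ADA is sampled after dosing only at Cycles 5 and 7, so a participant who stops before week 12 has no post-dose result for the incidence objective

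*Combined protocol and SAP*

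**What the plan says.** Table 8 (Section 3) lists, among the tertiary/exploratory objectives, "To assess the incidence of anti-drug antibodies (ADAs) against obinutuzumab", if applicable.

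- **Baseline.** Table 6 schedules one obinutuzumab ADA sample on Day -7, with the footnote "Samples should be taken BEFORE obinutuzumab is administered".
- **After dosing.** In Tables 2, 3 and 7 the obinutuzumab ADA row is marked at screening and in the Cycle 5 onwards column, and nowhere else. The footnote restricts the later mark: "Obinutuzumab ADA and PK samples to be taken only in Cycle 5 and 7 before administration of RO7172508" (y in Tables 2 and 3, x in Table 4). Table 7 reads "samples to be taken only in Cycle , 5 and 7 before administration of RO7172508", with a stray comma where a cycle number may have dropped out.
- **Off treatment.** In Tables 2, 3 and 7 the End of Treatment, Safety Follow-Up and Unscheduled cells are blank for this assay. The same tables schedule obinutuzumab PK at End of Treatment, and RO7172508 ADA at all three of those visits.
- **Coverage in the text.** Section 8.5.1: "Antibodies to obinutuzumab will be evaluated in all participants who receive obinutuzumab as pre-treatment according to the SoA". Section 9.4.5 makes a similar statement about all participants who receive obinutuzumab, without the reference to the SoA.
- **Analysis population.** Table 21 (Section 9.3), immunogenicity: "Participants who had at least one pre-dose and one post-dose ADA assessment will be included". No drug is named.

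The obinutuzumab rows of Table 4 are not legible in the copy reviewed, so only its footnote is relied on here.

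**The concern.** An incidence needs a post-dose result from the participants in its denominator. Here the first such result requires a participant to reach the Cycle 5 dose. The protocol foresees several routes off treatment before then: progression at the scan due within 7 days before Cycle 3 Day 1 or at the next one six weeks later, mandatory discontinuation for Grade 3 IRR/CRS, and toxicity that cannot be managed (Section 7.1). Section 8.3.8.4 also asks for discontinuation to be considered at once for events suspected to be ADA-related. The life-expectancy criterion is 12 weeks or more, the same horizon as the first post-dose sample.

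At stake is what the reported figure describes. It would be the incidence of obinutuzumab ADA among those still on RO7172508 at week 12, while Section 9.4.5 would lead a reader to expect all participants who received obinutuzumab. The numbers behind it would also be smaller than they need to be.

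**Working it through.** The documents give no sample size, precision or time on treatment for this objective, so there is no figure of the plan's own to reproduce. The steps below fix the timing from the documents and then illustrate the size under stated assumptions.

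**1. Timing.** Cycles are 21 days (schedule tables), and obinutuzumab starts on Day -7 (Section 6.1).
- C5D1 is 4 × 21 = 84 days, or 12.0 weeks, after C1D1 (Day 85). Counted from obinutuzumab, it is (84 + 7)/7 = 13.0 weeks.
- C7D1 is 6 × 21 = 126 days, or 18.0 weeks, after C1D1 (Day 127).

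These are the earliest dates. Section 6.6 treats late cycles as delayed rather than missed, so a delay moves the sample later.

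**2. Share with no post-dose result (assumed).** Take time to stopping as exponential with median m weeks, and a cut at 11.5 weeks, just before C5D1. The share reaching Cycle 5 is 0.5^(11.5/m).

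| Assumed median m | Reach Cycle 5 | No post-dose result |
|---|---|---|
| 6 weeks | 0.5^(11.5/6) = 26% | 74% |
| 8 weeks | 0.5^(11.5/8) = 37% | 63% |
| 12 weeks | 0.5^(11.5/12) = 51% | 49% |

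Moving the cut to 12.0 weeks gives 25%, 35% and 50%, so the exact cut hardly matters.

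**3. Effect on precision (illustration).** Suppose 15 participants receive obinutuzumab. This number is an assumption; the documents do not fix it.
- Evaluable n is 15 × 0.26 ≈ 4 at the low end and 15 × 0.51 ≈ 8 at the high end.
- With no positives, the upper limit of an exact 90% interval is 1 - 0.05^(1/n): 0.53 for n = 4, 0.31 for n = 8, and 0.18 if all 15 are evaluable.
- The chance of at least one positive at a true rate of 10% is 1 - 0.9^n: 0.34 for n = 4, 0.57 for n = 8, and 0.79 for n = 15. The same formula gives 0.41 for n = 5. The values for 15 and 5 agree with Section 9.2 and Table 20.

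The comparison with n = 15 assumes that every participant attends End of Treatment and that an early sample is as informative as a late one. It is therefore the most that the extra sample could gain.

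**4. Scope of the footnote.** In Tables 2 and 7, marker y sits on the Cycle 5 onwards cells, so its restriction to Cycles 5 and 7 applies to that column and leaves the other obinutuzumab PK samples intact. In Table 3 the marker is also on the row labels for obinutuzumab PK and ADA. Read literally there, it rules out the PK samples that the same row schedules in Cycles 1 to 4 and at End of Treatment.

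**The case against.** Several counter-arguments limit the point.

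- **Analysis population.** A reader might infer that early stoppers leave the immunogenicity population. Table 21 does not say so: it names no drug, and RO7172508 ADA is sampled from Cycle 1, so they can qualify through that assay. What they lack is the obinutuzumab result. This objection stands.
- **Contradiction with Section 8.5.1.** That sentence defers to the SoA, so it promises no more than the schedule delivers. Only Section 9.4.5 is unqualified, and even it does not expressly promise a post-dose result for everyone. This stands in large part.
- **Samples at discontinuation.** Section 8.5.1 asks for additional ADA samples at discontinuation or safety follow-up and names no drug. But the sentence sits in the RO7172508 paragraph and is paired with a RO7172508 concentration. If it is meant to cover obinutuzumab, the schedule rows should show it, so an edit is needed either way.
- **Bias.** It is tempting to say that the incidence would be too low because ADA-positive participants stop early. No passage links obinutuzumab ADA to early stopping. Section 4.3.2 reports, for other compounds, no ADA up to 32 weeks in five pre-treated patients. By analogy, early End of Treatment samples could be mostly negative, and adding them could itself lower the estimate. The direction is unknown.
- **Size.** To call those reaching Cycle 5 a minority is an assumption: the 12-week scenario gives 51%. Section 7.1 also allows treatment beyond RECIST progression, so a progressing scan need not end sampling.
- **Consequence.** No stated decision uses obinutuzumab ADA incidence. Section 4.1.3 bases implementation on loss of RO7172508 exposure or on ADA-related safety events. This stands and sets the priority.

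**Conclusion.** The gap is real but minor. In Tables 2, 3 and 7 a participant who stops before Cycle 5 has no post-dose obinutuzumab ADA result, so the incidence objective would be answered only in those on treatment at week 12 or later. Table 4 carries the same footnote; its row should be checked. About half to three-quarters of obinutuzumab-treated participants would have no result under assumed exponential medians of 6 to 12 weeks. That range is an illustration, because the documents give no time on treatment.

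Three stronger readings do not hold: that these participants drop out of the immunogenicity population, that the estimate is biased in a known direction, and that the footnote conflicts with End of Treatment PK in every table (the conflict shows only in Table 3). Priority is low, because the objective is exploratory and applies only if obinutuzumab is implemented.

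**What to change.** 1. Mark the obinutuzumab ADA row at End of Treatment in the Part II schedules (Tables 2, 3 and 7, and Table 4 if its row lacks it). Run the assay on the serum drawn at that visit for obinutuzumab PK and RO7172508 ADA.
2. In Section 9.4.5, state that obinutuzumab ADA incidence is summarised with sampling time shown, with the number of treated participants who have no post-dose result. Early End of Treatment samples may be less informative than those at Cycles 5 and 7 and should not be pooled with them unlabelled.
3. Attach the footnote limiting samples to Cycles 5 and 7 to the Cycle 5 onwards cells alone. In Table 3, remove it from the row labels so that it no longer contradicts the other obinutuzumab PK samples.
4. Reconcile the stray comma in the Table 7 footnote, and say whether a cycle number is missing.

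The cost is one extra assay per obinutuzumab-treated participant on blood already drawn, plus wording changes. No visit or procedure is added.
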